13.4.2. Reporting Adverse Events to the Responsible IEC/IRB and Health Authorities

Adverse events that meet the IEC/IRB requirements for reporting must be reported within the IEC/IRB's written guidelines. Each clinical site will refer to and follow any guidelines set forth by their Approving IEC/IRB. Each clinical site will refer to and follow any guidelines set forth by their local governing Health Authorities.

The Sponsor will report applicable Adverse Events to the local health authorities according the written guidelines, including reporting timelines.

13.5. Events of Special Interest

None identified.

Clinical Study Protocol

Johnson & Johnson Vision Care, Inc.

13.6. Reporting of Pregnancy

Subjects reporting pregnancy (by self-report) during the study will be discontinued after the event is recorded as an Adverse Event. Once discontinued, pregnant participants and their fetuses will not be monitored for study related purposes. Pregnant participants are not discontinued from contact lens or solution related studies for safety concerns, but due to general concerns relating to pregnancy and contact lens use. Specifically, pregnant women are discontinued due to fluctuations in refractive error and/or visual acuity that occur secondary to systemic hormonal changes, and not due to unforeseen health risks to the mother or fetus.

14. STATISTICAL METHODS

This section is a general outline of the statistical methods that will be implemented in this clinical trial. More details will be included in the stand-alone Statistical Analysis Plan (SAP). The standalone SAP will be finalized and signed prior the database lock and unmasking.

14.1. General Considerations

Statistical Analysis will be undertaken by the sponsor or under the authority of the sponsor. A general description of the statistical methods to be implemented in this clinical trial is outlined below.

All data summaries and statistical analyses will be performed using the SAS software version 9.4 or higher (SAS Institute, Cary, NC, USA).³² Throughout the analysis of data, the results for each subject/eye will be used when available for summarization and statistical analysis. Unscheduled visits will be summarized separately and will be excluded from the statistical analysis.

Summary tables (descriptive statistics and/or frequency tables) will be provided for all baseline variables, efficacy variables and safety variables as appropriate. Continuous variables will be summarized with descriptive statistics (n, mean, standard deviation [SD], median, minimum and maximum). Frequency count and percentage of subjects or eyes within each category will be provided for categorical data.

14.2. Sample Size Justification

This study was designed and powered to demonstrate non-inferiority of the Test lens (EMO-200) compared to the Control lens (EMO-118) with respect to monocular distance logMAR visual acuity under bright HLHC and lens fit acceptance after 10-minute lens settling period. The ample size was calculated for both the primary and secondary endpoints to achieve a minimum statistical power of 80% using a 2-sided type I error of $\alpha=0.05$ based on historical data from [REDACTED] [REDACTED] was a 2×2 crossover study with two study lenses (EMO-116 and EMO-118). In [REDACTED] all eyes had acceptable lens fit. Table 6 below presents the descriptive statistics of monocular logMAR visual acuity under bright HLHC at fitting observed from [REDACTED].

Clinical Study Protocol

Johnson & Johnson Vision Care, Inc.

Table 6: Descriptive Summary of Monocular LogMAR Visual Acuity Post Lens-Fitting from [REDACTED] – Per Protocol Subjects

	EMO-116	EMO-118
Number of eyes	50	50
Mean (SD)	-0.03 (0.098)	0.01 (0.082)

SD = standard deviation

Monocular Distance logMAR Visual Acuity

The sample size estimate for monocular distance logMAR visual acuity was calculated using a linear mixed model-based power analysis method³³. The model included lens, period, and lens wear sequence as fixed effects. An unstructured (UN) covariance matrix was used to model the residual errors between measurements within the same subject and eye across study periods. It was assumed there was no difference between the Test and Control lenses since the two study lenses have not been evaluated in the same study previously. Sample size estimation was carried out using an approximation of the power of an F-test derived from the non-centrality parameter calculated from the observed F statistic of the linear mixed model. Below is the variance-covariance matrix used in the sample size calculation for monocular logMAR visual acuity.

Subject intercept: 0.003087

The UN covariance matrix:
$$\begin{bmatrix} 0.004953 & -0.00076 \\ -0.00076 & 0.005157 \end{bmatrix}$$

Lens Fit Acceptance

Acceptable lens fit is a binary response as $Y = 1$ if a subject eye has an acceptable fit and $Y = 0$ otherwise. Indicated by the historical data from [REDACTED] there was no unacceptable lens fitting for both study lenses. Assuming no difference between study lenses and a correlation of 0.80 between left and right eyes within the same subject and period; and a correlation of 0.50 between measurements within the same subject across periods, a total of 2000 replicating trials were simulated with a reference (Control lens) rate of 95% (worse-case scenario) for lens fit acceptance. Given the rare event binary outcome of fit acceptance (i.e., the number of unacceptable fit is very small), each replicated sample was analyzed using a Bayesian beta-binomial model with correlated binary data (Diniza et al; 2010).³⁴ Sample size was estimated to achieve a minimal statistical power of 80% with a non-inferiority margin of -10% (Test – Control). Table 7 summarizes the required number of subjects for each of the primary and secondary endpoints to achieve a minimum of 80% statistical power with a 2-sided type I error of 0.05.

Table 7: Sample Size and Power for the Primary and Secondary Endpoints

Endpoints	Test/Margin	Sample size	Power
Monocular LogMAR VA	Non-inferiority (0.05)	28	92%

Clinical Study Protocol

Johnson & Johnson Vision Care, Inc.

Lens Fit Acceptance	Non-inferiority (-10%)	56	81%
---------------------	------------------------	----	-----

As indicated in Table 7 above, the sample size chosen for this study was primarily driven by lens fit acceptance in order to achieve a statistical power of at least 80% for both primary and secondary endpoints. The plan is to enroll approximately 67 subjects with a target of 56 to complete the study.

14.3. Analysis Populations

The following analysis populations will be defined and used in the analysis and presentation of the data.

All Enrolled:

All Enrolled Population includes all subjects with recorded data in the electronic Case Report Form (eCRF) database.

Intent-To-Treat (ITT):

Intent-to-treat will include all the subjects who were randomized to study treatment. Subjects will be analyzed as per randomized treatment. At least one observation should be recorded. Subjects with major protocol deviations, including, but not limited to non-compliant to protocol specified lens wear time requirements, ineligible subjects who were inadvertently randomized and primary endpoint measurements collected without or with non-valid device verifications, etc., will be included in the ITT analyses.

Safety Population:

All subjects who were administered any test article excluding subjects who drop out prior to administering any test article. At least one observation for safety endpoints should be recorded (e.g., ocular symptom, slit-lamp finding, etc.) on or after treatment start date. Subjects will be analyzed as per treatment received.

Per Protocol (PP)

All subjects who have completed the study and did not substantially deviate from the protocol as determined by the trial cohort review committee prior to database hard lock. Justification of excluding subjects with protocol deviations in the per-protocol population set will be documented in a memo to file. See Section 10 for definition and examples of major deviations.

14.4. Level of Statistical Significance

All planned analysis for this study will be conducted with an overall type I error rate of 5%.

14.5. Primary Analysis

Non-inferiority of Test compared to Control with respect to the primary endpoint of monocular logMAR visual acuity will be assessed on the Per-protocol population (PP).

Clinical Study Protocol

Johnson & Johnson Vision Care, Inc.

Monocular Distance logMAR Visual Acuity (VA)

Monocular distance logMAR VA under bright HLHC will be analyzed using a linear mixed model to compare the Test and Control lenses after a 10-minute lens setting period. The model will include lens type, lens sequence, and period as fixed effects. Other subject characteristics such as age, gender and race will be included as fixed covariates when appropriate. Site and subject will be included in the model as random effects (G-side). The covariance of residuals between measurements on the same eye across periods within the same subject (R-side) will be modeled using Unstructured (UN) covariance structure. If the model does not converge, then other covariance structures, such as compound Symmetry (CS) covariance structure, will be considered. The Kenward and Roger method (Kenward & Roger, 1997)³⁵ will be used for the denominator degree of freedom.

Hypothesis Testing

The null and alternative hypotheses for testing non-inferiority of the Test lens relative to the Control lens with respect to logMAR visual acuity are as follows:

$$\begin{aligned} H_0: \mu_T - \mu_C &\geq 0.05 \\ H_A: \mu_T - \mu_C &< 0.05 \end{aligned}$$

Where, μ_T represents the mean logMAR VA score for the Test lens and μ_C represents the mean logMAR VA score for the Control lens. Non-inferiority will be declared if the upper bound of the 2-sided 95% confidence interval of the difference (Test – Control) is less than 0.05.

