1.12	Eligibility Following Baseline Evaluation	
All responses to Inclusion Criteria questions must be answered “yes” and all responses to Exclusion Criteria questions must be answered “no” for the subject to be considered eligible.
 
Note: If subject is deemed to be ineligible after baseline, proceed to Final Evaluation and complete Subject Disposition. Refraction and Biomicroscopy forms do not need to be completed as part of Final Evaluation.
	[REDACTED]

Visit 1: Treatment 1 Lens Fitting			
Step	Procedure	Details	[REDACTED]
1.13	Lens Selection	
Assign the study lens based on the lens fitting schedule. Record the randomization ID.
 
Select the contact lens power based on subjective best sphere refraction.
	[REDACTED]
1.14	Lens Insertion	
The investigator or the subject inserts the study lenses. Record the time of lens insertion.
 
Check for lens damage under the slit lamp before proceeding with lens settling.
 
Replace damaged lenses if applicable.
 
Ensure the subject is given a Patient Instruction Guide.
	[REDACTED]

Clinical Study Protocol
Johnson & Johnson Vision Care, Inc.

Visit 1: Treatment 1 Lens Fitting			
Step	Procedure	Details	
1.15	Lens Settling	Allow the study lenses to settle for a minimum of 10 minutes.	
1.16	Subjective Lens Fit Assessment	
Evaluate overall lens fit acceptance (acceptable or unacceptable) based on centration, movement and other fitting characteristics.
 
An unacceptable fit is deemed by one of the following criteria:
 
 • limbal exposure at primary gaze or with extreme eye movement; • edge lift; • excessive movement in primary and up gaze; or • insufficient movement in all three of the following conditions: primary gaze, up gaze, and Josephson push up. 
Note: if lens fit is unacceptable, the subject will skip Steps 1.17 to 1.22, and proceed with Step 1.23 and Treatment 2 Lens Fitting. The subject will be discontinued after Subjective Lens Fit Assessment for the Treatment 2 has been completed.
	
1.17	Over the Lens Distance Snellen VA	Record the subject's distance visual acuity to the nearest letter with the study lenses (OD, OS).	

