1.20	Distance ETDRS LogMAR Visual Acuity	Perform monocular distance ETDRS LogMAR visual acuity test at a 4-meter distance with the subject wearing the study lenses under the following conditions:	

Clinical Study Protocol
Johnson & Johnson Vision Care, Inc.

Visit 1: Treatment 1 Lens Fitting			
Step	Procedure	Details	
		
 1. dim illumination (1.4-1.6 lux, or -0.8--0.6 EV), low luminance (2.5-2.8 cd/m², or 4.3-4.5 EV), with high contrast charts (LLHC); 2. bright illumination (686-788 lux, or 8.1-8.3 EV), high luminance (181-208 cd/m², or 10.5-10.7 EV) with low contrast charts (HLLC); 3. bright illumination (686-788 lux, or 8.1-8.3 EV), high luminance (181-208 cd/m², or 10.5-10.7 EV) with high contrast charts (HLHC); 
The Precision Vision 4-meter high (Charts 1 – 4) and low contrast (Chart 1 and 2) ETDRS charts will be used.
 
One measurement per condition for OD and OS, respectively.
	
1.21	Visual Experience	Encourage the subjects to look at objects at distant and near, and if possible, under bright and dim lighting conditions.	
1.22	Subject Reported Ocular Symptoms	Subjects will respond to a verbal open-ended symptoms questionnaire regarding the study lens.	
1.23	Study Contact Lens removal	Subjects remove and discard the study contact lenses.	

Visit 1: Treatment 2 Lens Fitting

Allow 15 minutes of washout period with the subjects wearing their habitual correction before proceeding to Treatment 2 Lens Fitting. If the subject wears habitual soft contact lens to the visit, instruct the subject to remove own lenses and store them temporarily in a lens case (provided by the investigator) with saline before continuing with Treatment 2 Lens Fitting.

Repeat all steps under Treatment 1 Lens Fitting for the second trial lens, per the randomization scheme.

FINAL EVALUATION

The final evaluation will take place immediately following the completion of Visit 1 per the study protocol. It may also take place at any point the subject discontinues the study or is terminated from the study.

Clinical Study Protocol

Johnson & Johnson Vision Care, Inc.

In the event of an adverse event, Final Evaluation will be performed after all required follow-up of the adverse event is complete (see Section 13.3 for detailed instructions on follow-up of adverse events).

Final Evaluation			
Step	Procedure	Details	

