F.1	Final Exam Form	Indicate if the subject completed the study successfully. If subject discontinued from the study, indicate the reason.	
F.2	Exit Refraction	Perform bare-eye subjective spherocylindrical refraction with a phoropter and record the best-corrected distance visual acuity (OD and OS) to the nearest letter. Note: This step is not necessary if the subject was exited due to screen failure.	
F.3	Exit Slit Lamp Biomicroscopy	Slit Lamp Classification Scale per ISO 11980 will be used to grade the findings. If the clearance of the fluorescein needs to be expedited, preservative-free rewetting drops or saline may be instilled. Note: This step is not necessary if the subject was exited due to screen failure, or if biomicroscopy was performed as part of the final follow-up visit procedures (i.e., immediately prior to the final evaluation).	

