8. SUBJECTS COMPLETION/WITHDRAWAL

8.1. Completion Criteria

Subjects are considered to have completed the study if they:

- provided informed consent;
- are eligible;
- completed the study visit.

Clinical Study Protocol

Johnson & Johnson Vision Care, Inc.

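### Does restricting the acuity test to per-protocol completers hide the effect of unacceptable lens fits?

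*Combined protocol and SAP*

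**What the plan says.** Section 14.5 states that non-inferiority on bright, high-contrast acuity "will be assessed on the Per-protocol population (PP"). Section 14.3 defines that set as "All subjects who have completed the study and did not substantially deviate from the protocol". Section 8.1 begins "Subjects are considered to have completed the study if they" and lists three conditions: consent, eligibility and completion of the study visit.

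Step 1.16 of Section 7.2 says that "if lens fit is unacceptable, the subject will skip Steps 1.17 to 1.22, and proceed with Step 1.23 and Treatment 2 Lens Fitting". The skipped steps include the ETDRS acuity test at Step 1.20. The step goes on: "The subject will be discontinued after Subjective Lens Fit Assessment for the Treatment 2 has been completed". For the second period the instruction is "Repeat all steps under Treatment 1 Lens Fitting for the second trial lens", so the same rule applies to the second lens.

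Section 14.3 also defines an ITT set and says that subjects with major deviations "will be included in the ITT analyses". Section 14.5 uses PP, Section 14.6 uses the safety population for fit, and Section 14.7 names no set. Section 14.9 rules out imputation but requires missing values to be counted. At the final evaluation, Step F.1 adds "If subject discontinued from the study, indicate the reason". The opening of Section 14 calls itself an outline and leaves further detail to a stand-alone SAP, to be signed before database lock and unmasking.

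**The concern.** Membership of the primary analysis set appears to depend on an outcome of the lenses under comparison. One unacceptable fit removes the subject's acuity on that lens, and the discontinuation removes the subject from PP. When only the second lens fails, valid first-lens acuity is lost too. If Test fitted worse than Control and a poor fit also blurred vision, the subjects most unfavourable to Test would be missing from the test meant to detect poorer vision. Non-inferiority could then be declared on a favourably selected group, with no named analysis on a wider set to show it.

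**Working it through.** **Inputs.** Section 14.2 gives residual variances 0.004953 and 0.005157, covariance -0.00076, margin 0.05, a worst-case fit acceptance of 95%, and fit correlations of 0.80 between eyes and 0.50 across periods. Target: 56 completers from about 67 enrolled. The acuity cost of a poor fit is not in the documents; 0.05 to 0.20 logMAR is assumed.

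**Reproducing Table 7.** Variance of the Test-Control difference per eye = 0.004953 + 0.005157 + 2 × 0.00076 = 0.01163. With two eyes and independent residuals, the variance per subject is 0.01163/2 = 0.005815. At 28 subjects SE = √(0.005815/28) = 0.0144 and 0.05/0.0144 = 3.47. The noncentral F gives power of 91.6% (26 df) to 92.6% (54 df), against the stated 92%.

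**How many subjects are affected.** The chance that at least one eye fails in a given period = 1 - (0.95² + 0.80 × 0.95 × 0.05) = 0.0595. Over both periods it lies between 5.95% and 11.9%. A Gaussian-copula simulation with the stated correlations gives 8.6%. Section 8.2 replaces subjects who discontinue early, so these come on top of the 56: 56/(1 - 0.086) = 61.3, or roughly 5 of 61. Even at 51 subjects acuity power would be 99.6%, so the issue is selection and not power.

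**How large a Test excess can still pass the fit test.** This uses the mixture likelihood of Section 14.6 on a grid, with 56 subjects (112 eyes per lens), the stated priors for the coefficients and ρ, no subject or site random effects, and failures bilateral where possible. A pass needs a posterior probability of at least 0.975.

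| Failed eyes, Control/Test | Posterior probability | Excess if passed |
|---|---|---|
| 6/7 | 0.975 (borderline) | 1/112 = 0.009 |
| 5/7 | 0.980 | 2/112 = 0.018 |
| 5/8 | 0.972 (fails) | – |
| 2/5 | 0.980 | 3/112 = 0.027 |
| 1/6 | 0.977 | 5/112 = 0.045 |
| 0/4 | 0.988 | 4/112 = 0.036 |
| 0/5 | 0.974 (fails) | – |

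Under the failure patterns most favourable to passing, the excess reaches about 0.054.

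**Hidden shift = excess × cost.** Smallest: 0.009 × 0.05 = 0.0005 logMAR. Largest in the table: 0.045 × 0.20 = 0.009. Largest overall: 0.054 × 0.20 = 0.011, which is 0.011/0.05 = 22% of the margin. It could matter only if the PP upper bound were already at 0.05 - 0.011 = 0.039 or above.

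**Where the bound is expected.** At 56 subjects SE is 0.0102 if eyes are independent and 0.0144 if fully correlated. With an observed difference of zero, the upper bound is 1.96 × SE = 0.020 to 0.028.

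**Tipping check.** Suppose 5 of 56 subjects are unmeasured, have mean difference *d*, and the other 51 average zero. The bound is 5*d*/56 + 1.96 × √[(s² + 0.0828*d*²)/56], where 0.0828 = (5 × 51/56)/55 carries the spread between the two groups.
- Independent eyes, s² = 0.005815: *d* = 0.25 gives 0.0223 + 0.0275 = 0.050.
- Fully correlated eyes, s² = 0.01163: *d* = 0.20 gives 0.0179 + 0.0320 = 0.050.

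So *d* must be about 0.20 to 0.25. With 5 of 61, where the factor is (5 × 56/61)/60 = 0.0765, the same formula gives about 0.23 to 0.28. Inclusion criterion 7 equates 0.20 logMAR with two lines. At the assumed maximum cost of 0.20, an average of even 0.20 would need all five subjects to fail in both eyes with Test and in neither eye with Control. That is 10 failed eyes against 0, while the table shows 5 against 0 already failing the fit test.

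**The case for a change.** The strongest contrary argument comes from Section 4.2, which says that a departure of EMO-200 from its intended design would show up in vision, in fit, or in both. On that view fit failures are the subjects in whom poorer vision is most likely. Replacing them under Section 8.2 refills the 56 with subjects whose lenses fitted. A supportive analysis would also cost little, and Section 14.3 shows that ITT analyses were intended.

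The reading of the text largely stands, with one qualification. No section says outright that a subject discontinued for fit is outside PP: Section 8.1 asks only for a completed visit, and Section 8.2 tells the investigator to complete the current visit for discontinued subjects. Exclusion is the likely reading but remains an inference. It is also true that Section 14 does not say which endpoint the ITT analyses cover.

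The argument does not show that the conclusion is at risk. An ITT rerun could not supply acuity on a lens that was never tested. At 95% acceptance it would recover about 1.5 of 56 subjects, those failing only in the second period, each with acuity on one lens and so little information on the within-subject contrast. Imputing acuity for failed lenses would address a different question from the one in Section 14.5, and fit failure is already judged directly.

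**Conclusion.** The concern is right about the wording but does not call for a change. Exclusions for fit will be visible through recorded discontinuation reasons and counts of missing values. A worse-fitting Test lens is tested on the safety population in a hypothesis that Section 2.3 makes necessary for success. The effect on acuity is nil if no fit fails, as Section 14.2 reports for the historical study, and has no net direction if both lenses fail equally often. Otherwise it is about 0.0005 to 0.011 logMAR, against room of roughly 0.02 to 0.03 between the expected upper bound and the margin.

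This rests on the assumed cost of 0.05 to 0.20 logMAR, on the planning variances, on an observed difference near zero, and on a fit model without random effects; including those effects could raise the largest passing excess. Which endpoint the ITT analyses cover is detail that Section 14 leaves to the stand-alone SAP, which is not among the documents reviewed and may already state it. An analyst would naturally apply the Section 14.5 model to that set. Following the plan as written still gives a sound conclusion.

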4. STUDY DESIGN AND RATIONALE

4.1. Description of Study Design

This is a multi-center, randomized, controlled, double-masked, 2x2 cross-over, non-dispensing study. Each subject will be bilaterally fitted with one of the two test articles in each of the two periods during a single visit, which includes:

Visit 1: Subject screening, baseline evaluation, randomization, lens fit #1 and #2, and final evaluation

If a subject meets all edibility criteria, then they will be randomized to one of two lens wear sequences. Subjects will be fitted in a bilateral fashion in their first study lens per the randomization scheme. Study assessments will be performed on the first lens. After undergoing all assessments, the first study lens will be removed, and subjects will have a 15-minute washout period prior to be fit with their second lens per the randomization schedule. Study assessments will be conducted while wearing the 2nd study lens and final evaluations will be performed.

Study participants will have no access to test articles at study closure.

Clinical Study Protocol

Johnson & Johnson Vision Care, Inc.

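### The primary acuity model treats the two eyes' Test-Control differences as uncorrelated; if they are positively correlated, the non-inferiority interval is too narrow

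*Combined protocol and SAP*

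**What the plan says.** Protocol Section 14.5 fits a linear mixed model to monocular bright high-contrast logMAR acuity, with one measurement per eye per lens. On fixed effects: "The model will include lens type, lens sequence, and period as fixed effects". On random effects: "Site and subject will be included in the model as random effects (G-side"). The residual part is "The covariance of residuals between measurements on the same eye across periods within the same subject (R-side"), taken as unstructured (UN). The fallback reads: "If the model does not converge, then other covariance structures, such as compound Symmetry (CS) covariance structure, will be considered". Non-inferiority is declared if the upper limit of the two-sided 95% interval for Test minus Control is below 0.05 logMAR.

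The sizing model in Section 14.2 has the same structure, a subject intercept plus a 2x2 matrix: "An unstructured (UN) covariance matrix was used to model the residual errors between measurements within the same subject and eye across study periods". Its inputs come from a "crossover study with two study lenses (EMO-116 and EMO-118"), with 50 eyes per lens in Table 6. Table 7 gives 92% power with 28 subjects for acuity. Section 14.2 adds that "the sample size chosen for this study was primarily driven by lens fit acceptance", which needs 56 completers.

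Fitting is bilateral (Section 4.1): "Subjects will be fitted in a bilateral fashion in their first study lens per the randomization scheme".

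**The concern.** Anything that affects a child during one lens period, such as attention, response criterion or tiredness, can move both eyes' acuity together in that period. So can a child-specific response to one lens type, because both eyes wear the same lens. Either would correlate the two eyes' Test-Control differences. The subject intercept does not capture this, because it is common to both periods and cancels from every difference. The per-eye residual matrix does not capture it either, because it never links the right eye to the left.

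The model therefore counts 2N independent differences from N children. If the differences are positively correlated, the interval is too short and the chance of declaring non-inferiority at the margin exceeds 2.5%. The upper limit of that interval is the whole primary decision. Kenward-Roger degrees of freedom do not repair a missing covariance term, and compound symmetry applied per eye leaves it missing.

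**Working it through.** **Inputs (Section 14.2).** Subject variance 0.003087; residual variances 0.004953 and 0.005157; residual covariance across periods -0.00076; margin 0.05; assumed true difference 0; N = 28 (Table 7) and N = 56 completers. The correlation r is not given, so a range of 0 to 1 is shown.

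**1. What the model implies.** Every covariance between a right-eye and a left-eye measurement in one subject equals the subject variance s², whether in the same period or in different periods. Hence Cov(d_OD, d_OS) = s² - s² - s² + s² = 0, so r is zero by construction.

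**2. Reproducing Table 7.** Variance of one eye's difference: D = 0.004953 + 0.005157 + 2(0.00076) = 0.01163. With 56 independent eye differences from 28 subjects, SE = sqrt(0.01163/56) = 0.01441. Noncentral-t power against 0.05 is 91.6% with 26 df and 92.6% with 54 df, matching the stated 92%. With r = 1 the same calculation gives 65.6%, so the published figure rests on r = 0.

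**3. Effect of r.** True SE = sqrt(D(1+r)/(2N)), while the model reports sqrt(D/(2N)). One-sided type I error is Φ(-1.96/sqrt(1+r)). Corrected intervals use N - 2 df.

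| | r = 0 | r = 0.26 | r = 0.5 | r = 1 |
|---|---|---|---|---|
| Type I error, planned interval | 2.5% | 4.0% | 5.5% | 8.3% |
| Coverage of nominal 95% interval | 95% | 92% | 89% | 83% |
| True SE, N = 28 | 0.01441 | 0.01618 | 0.01765 | 0.02038 |
| N = 28: planned interval passes | 92% | 90% | 89% | 85% |
| N = 28: corrected interval passes | 92% | 84% | 78% | 66% |
| N = 56: corrected interval passes | 99.8% | 99% | 98% | 93% |
| N = 56: corrected half-width (planned 0.0202) | 0.0204 | 0.0229 | 0.0250 | 0.0289 |

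The pass rates assume no true difference.

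**4. Simulation.** In 100,000 trials at N = 56, treating eye differences as independent gave type I error of 2.5%, 4.1%, 5.7% and 8.4% at the four values of r. The two-eye-mean analysis gave 2.5% throughout. REML fits of the planned model (N = 56, without site or covariates, 110 df, 2,500 per value) gave 2.2%, 4.4% and 6.2% at r = 0, 0.26 and 0.5, with Monte Carlo error of 0.3 to 0.5 points. In a separate set of 1,500 fits per value, the mean model SE stayed at about 0.010 for every r, so fitting does not correct the problem.

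**5. What the documents suggest about r.** The same-eye covariance across periods is 0.003087 - 0.00076 = 0.002327, which is below the fitted fellow-eye covariance of 0.003087. The fitted subject variance is approximately the average of the within-period and cross-period fellow-eye covariances. Assume there is no persistent eye-specific variance, so that the cross-period fellow-eye covariance is also 0.002327. The within-period one is then 2(0.003087) - 0.002327 = 0.003847, and r = 2(0.003847 - 0.002327)/0.01163 = 0.26. This is a moment estimate, not a bound. In 1,000 simulated samples of 25 subjects with no omitted term, the off-diagonal had SD 0.00088, and 19.7% of samples gave -0.00076 or lower.

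As an analogy only, the lens-fit sizing in Section 14.2 assumes a correlation of 0.80 between eyes within a period and 0.50 across periods. If the 0.50 covers both same-eye and fellow-eye pairs with equal variances, those values imply r = (0.80 - 0.50)/(1 - 0.50) = 0.6 for that endpoint.

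**The case against.** The strongest reply is that r is unknown. The one documentary clue lies within a standard error of zero and comes from a different lens pair in about 25 subjects. The two lenses here are described as the same in optical design, material, diameter and base curve, which weakens a child-specific lens effect as a source of correlation. If r were negative, the interval would be too wide. All of this stands, and it is why the conclusion is conditional on r. It does not remove shared variation between periods, and the model cannot show whether that variation is present.

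The r = 1 column is a mathematical limit. With the other planning values held, it needs fellow-eye correlations of about 0.74 within a period and 0.02 across periods, beside a same-eye cross-period correlation of about 0.29. It should be read as a ceiling.

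The practical effect is small if the lenses are truly equal. At 56 completers the planned and corrected decisions then differ with probability of about 0.4% at r = 0.26 and 1.4% at r = 0.5. That is correct, but the error rate is defined at the margin, and there it is inflated.

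Finally, Section 14 calls itself an outline and defers detail to a stand-alone SAP that is not among the documents reviewed. That SAP could add the missing term. However, Sections 14.2 and 14.5 both state the present structure, so a reader would expect the SAP to carry it forward.

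**Conclusion.** The concern holds. As written, the primary model sets r to zero, and Table 7's 92% depends on that. If r > 0, the standard error is understated by sqrt(1+r), at most 1.41, and one-sided false non-inferiority exceeds 2.5%: 4.0% at r = 0.26 and 5.5% at r = 0.5, with a ceiling of 8.3%. These figures rest on the Section 14.2 variances and on an assumed r. The existence of the restriction follows from the model alone.

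This is a matter of the validity of the primary interval, not of sample size. It should be fixed before unmasking, but it does not threaten the feasibility of the trial.

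**What to change.** Specify one of these in Section 14.5 and the stand-alone SAP:

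1. Keep the planned model and add a random subject-by-period effect, for example `RANDOM intercept period / SUBJECT=subject` with period as a class variable. The term is identifiable alongside the per-eye UN matrix.
2. Replace the subject intercept and per-eye matrix by a 4x4 eye-by-period covariance within subject.
3. Analyse the mean of the two eyes per subject and period in a standard 2x2 crossover model.

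Name option 3 as the non-convergence fallback in place of per-eye compound symmetry. Under Table 7, state that 92% at 28 subjects assumes independent eye differences, and give the corrected power over a range of r.

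The cost is a few sentences and a small change of code. The targets of 56 completers and about 67 enrolled need not change. If r = 0, option 3 widens the interval by about 1% (half-width 0.0202 to 0.0204). Option 1 widens it by about 3% on average, because its variance component cannot go below zero; approximate simulations put its type I error at 2.2% to 2.5%. Option 2 was not simulated. If r > 0, the standard error grows by 12% at r = 0.26, 22% at 0.5 and 41% at 1. At 56 completers the half-width is then still at most 0.0289 against the 0.05 margin.
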